#### **8.4. Data sources**

The data will be obtained retrospectively from hospital medical records, this study will not impose any additional procedures, assessments or changes to the routine management of subjects. The data will be transcribed to an anonymous e-CRF.

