Nonetheless NOACs were categorized as a second line treatment due to the restriction of SUKL (local regulatory authority) in Czech Republic and therefore Czech patients are primarily treated with warfarin (including patient post stroke/TIA) and NOACs treatment can be initiated only in case of defined contraindication. Czech Cardiology Society, Society of Ambulatory Specialist together with main Czech Public Insurance House (VZP) defined number of conditions where safe and efficacious anticoagulation therapy by VKA cannot be adequately ensured. Prescription of NOACs as first line therapy is allowed in these defined situations . One of the situations is described as higher sensitivity to warfarin. There are two variants of two genes, CYP2C9 and VKORC1, account for 30-50% of the variability in dosing of warfarin. The prevalence of CYP2C9 (allele \*1, \*2 and \*3) and VKORC1 (-1639 G and A alleles), and their combinations in Czech population was analyzed and about 30% of the Czech healthy subjects have genetically determined higher sensitivity to warfarin. Individuals with higher sensitivity to warfarin are eligible for first line NOACs treatment in secondary prevention of stroke.

Additionally there is no healthcare resource use (hospitalization days, outpatient visits, and clinical events) comparison of apixaban to warfarin available in the Czech Republic. The most intensive resource use is expected in the first 6 months after stroke, especially because of a high risk of the event recurrence. Considering that there are less outpatient visits, less monitoring needed and lower risk of the complications and adverse events expected with apixaban. Real-world data about the impact of different treatment strategies on healthcare resource use and costs are essential arguments for establishing the clinical value of new therapies.

In the light of this situation we have designed this study to compare the healthcare resource use in patients who use warfarin or apixaban in secondary stroke prevention as a first line therapy.

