## 8. RESEARCH METHODS

### 8.1. Study design

This is a double arm, non-interventional, single-center retrospective study according to Czech legal definitions (Law 378/2007 Sb.). For the description of the direct costs related to warfarin/apixaban treatment, retrospective data will be used for both, the warfarin treatment arm and the apixaban treatment arm.

The study follows two cohorts of NVAF patients, who used either warfarin or apixaban as a secondary stroke/TIA prevention.

The data to be collected retrospectively:

- Consecutive data of the 6 months after the first prescription of warfarin/apixaban (indicated as a secondary stroke/TIA prevention).

Considering the retrospective design of data collection, the non-interventional study will not impose any additional procedures, assessments or changes to the routine management of subjects. Data for the study will be obtained from clinical practice records and transcribed to an anonymous electronic case report form (e-CRF).

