## 8.2. Setting

In total, this non-interventional study follows the population of 240 patients with nonvalvular atrial fibrillation. From 240 NVAF patients, 120 patients are treated with warfarin and 120 patients are treated with apixaban.

The study will follow the period of 6 months after the prescription of warfarin or apixaban for the secondary stroke/TIA prevention.

The data will be collected retrospectively from clinical practice hospital records.

It's expected that the data will be collected within 3 months from the start of the study – the data collection will be closed as soon as there are 120 patients enrolled in each study arm. If there are not 120 patients enrolled in each study arm after 3 months of the data collection, the period can be prolonged up to 6 months from the start of the study.

Requirements for the center's eligibility are as followed: center able to genetically determine patients' higher sensitivity to warfarin; neurologists, who work in cerebrovascular center in a hospital; satisfactory experience in the care of patients with NVAF and treatment with warfarin and NOAC; sufficient number of patients with NVAF diagnosis fulfilling eligibility criteria.

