### 8.2.1. Inclusion criteria

The data will be collected for patients who have met all of the following inclusion criteria:

1. Diagnosis of non-valvular atrial fibrillation (NVAF);
2. New initiation of anticoagulation therapy (apixaban or warfarin) due to the ischemic event (stroke/TIA) meaning patients previously not anticoagulated due to diagnosis of NVAF;
3. Indication to anticoagulation therapy as a secondary stroke prevention within 7 to 30 days after the stroke/TIA event;
4. Apixaban arm: genetically determined higher sensitivity to warfarin;
5. Patients whose status allowed oral treatment with apixaban/warfarin;
6. Age  $\geq 18$ ;
7. Access to patient's records of the first 6 months of the warfarin/apixaban treatment.

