### 8.3. Variables

**Table 1:** Table of variables

Variable	Role	Data source(s)	Operational definition
Age, Sex, BMI, date of index event (stroke/TIA diagnosis), date of indication to warfarin/apixaban treatment (index date)	Demographic data	Medical records	Specified in e-CRF
CHA2-DS2-Vasc score, HAS-BLED score	Outcome	Medical records	Specified in e-CRF
Therapy after index event, prior to warfarin/apixaban treatment	Exposure	Medical records	Specified in e-CRF
Warfarin/apixaban therapy information (dosage; number of INR measurements in warfarin arm)	Exposure	Medical records	Specified in e-CRF
Number and type of resource use during the first 6 months of warfarin/apixaban treatment (outpatient visits, diagnostic procedures, labs, medication, hospital admissions)	Outcome	Medical records	Specified in e-CRF
Amount, type, severity and cost of ischemic events	Outcome	Medical records	Specified in e-CRF

Amount, type, severity and cost of major/minor hemorrhagic events	Outcome	Medical records	Specified in e-CRF
Adverse events	Outcome	Medical records	Specified in e-CRF

*Index date = The index date will be the first date of OAC prescription indicated for secondary stroke/TIA prevention.*

*Index event = The index event will be the first stroke/TIA event based on which the OAC treatment will be initiated.*

*Index event date = The index event date will be the date of first stroke/TIA event based on which the OAC treatment will be initiated*

*Therapy after index event, prior to warfarin/apixaban treatment (Aspirin, clopidigrel, Trombolytics (rhu-tPA - alteplase, urokinase), Anticoagulants (heparin, heparinoids), other)*

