##### **8.6.1. Case Report Forms (CRFs)/Data Collection Tools (DCTs)/Electronic Data Record**

As used in this protocol, the term CRF should be understood to refer to either a paper form or an electronic data record or both, depending on the data collection method used in this study.

A CRF is required and should be completed for each included patient. The completed original CRFs are the sole property of Pfizer and should not be made available in any form to third parties, except for authorized representatives of Pfizer or appropriate regulatory authorities, without written permission from Pfizer. The investigator shall ensure that the CRFs are securely stored at the study site in encrypted electronic form and will be password protected to prevent access by unauthorized third parties.

The investigator has ultimate responsibility for the collection and reporting of all clinical, safety, and laboratory data entered on the CRFs and any other data collection forms (source documents) and ensuring that they are accurate, authentic/original, attributable, complete, consistent, legible, timely (contemporaneous), enduring, and available when required. The CRFs must be signed by the investigator or by an authorized staff member to attest that the data contained on the CRFs are true. Any corrections to entries made in the CRFs or source documents must be dated, initialed, and explained (if necessary) and should not obscure the original entry.

In most cases the source documents are the hospital or the physician's chart. In these cases, data collected on the CRFs must match those charts.

In some cases, the CRF may also serve as the source document. In these cases, a document should be available at the investigator site and at Pfizer that clearly identifies those data that will be recorded on the CRF, and for which the CRF will stand as the source document.

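### The plan names only one centre's hospital records as the cost source and does not say how care given elsewhere is identified or handled, so direct costs may be understated and the arm difference biased by an unmeasured amount

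*Combined protocol and SAP*

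**What the plan says.** Section 8.1 describes a "single-center retrospective study according to Czech legal definitions". The source is stated twice. Section 8.2 says: "The data will be collected retrospectively from clinical practice hospital records". Section 8.4 says: "The data will be obtained retrospectively from hospital medical records".

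Table 1 (section 8.3) lists medical records as the source for every variable. These include the "number of INR measurements in warfarin arm", the resource-use counts (visits, diagnostics, laboratory tests, medication, admissions) and the costs of ischemic and hemorrhagic events. Operational definitions are left to the e-CRF. No insurer, general practitioner, outside laboratory or other hospital is named as a source.

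Two passages could widen the source. Inclusion criterion 7 asks for "Access to patient's records of the first 6 months of the warfarin/apixaban treatment". Section 8.6.1, in general text on case report forms, says: "In most cases the source documents are the hospital or the physician's chart".

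The primary objective (section 7) is to describe 6-month direct costs of treatment in both arms; the cost comparison is secondary. The rationale (section 6) expects "less outpatient visits, less monitoring needed" with apixaban, alongside fewer complications. Section 8.7 analyses everyone enrolled and gives no rule for missing or outside care. Section 8.9 does not list incomplete capture as a limitation.

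**The concern.** The objective is worded as the direct cost of treatment, but the named source can show only what reached the records of one hospital. A patient may have INR checked, attend a clinic or be admitted somewhere else. If that care leaves no trace in the hospital record, a sum over the record is too low. This affects the primary description in each arm before any comparison is made.

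For the secondary comparison, the loss need not be equal. INR counts are planned only for warfarin, so a missed INR check lowers warfarin cost alone. Visits, admissions, strokes and bleeds treated elsewhere can be missed in either arm, and would also affect the secondary counts of hospital days and clinical events. Because nothing in the protocol measures capture, a reader of the final report could not tell a real cost difference from a difference in how much of each arm's care stayed at the centre.

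**Working it through.** The plan states no capture rate, INR frequency or unit price, so there is no figure to reproduce. The check has two parts.

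**1. The passages side by side.** Criterion 7 can be read in three ways.
- Broadly: all records of the 6 months, wherever held. This goes beyond the hospital-only source in sections 8.2 and 8.4.
- Narrowly: the hospital's own chart for those months can be opened. This is met even if much of the care took place elsewhere.
- As a selection rule: only patients whose whole course was followed at the centre. This agrees with section 8.4, but it is not stated and there is no plan to report it.

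The text does not choose between them, and none of the three comes with a completeness check.

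**2. What incomplete capture could do.** Only the 120 patients per arm (section 8.2) comes from the protocol. Contact numbers and capture shares below are assumptions.

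Missed INR checks per warfarin patient = M × (1 − c), where M is the true number in 6 months and c is the share held in the study hospital's records. Take M from 8 to 16:

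| Capture c | Missed per patient | Missed over 120 patients |
|---|---|---|
| 75% | 8 × 0.25 = 2 to 16 × 0.25 = 4 | 240 to 480 |
| 50% | 8 × 0.50 = 4 to 16 × 0.50 = 8 | 480 to 960 |
| 25% | 8 × 0.75 = 6 to 16 × 0.75 = 12 | 720 to 1,440 |

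For the arm difference, recorded difference = cW × MW − cA × MA (W warfarin, A apixaban). Assume MW = 12 and MA = 3 monitoring contacts, so the true difference is 9:

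| cW | cA | Recorded difference |
|---|---|---|
| 75% | 75% | 9 − 2.25 = 6.75 |
| 50% | 50% | 6 − 1.5 = 4.5 |
| 25% | 25% | 3 − 0.75 = 2.25 |
| 50% | 100% | 6 − 3 = 3.0 |
| 25% | 100% | 3 − 3 = 0 |
| 100% | 50% | 12 − 1.5 = 10.5 |
| 100% | 25% | 12 − 0.75 = 11.25 |

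The bias is −12 × (1 − cW) + 3 × (1 − cA). It turns positive once the share missed on apixaban exceeds 12/3 = 4 times the share missed on warfarin. Under these assumptions the difference shrinks in most scenarios, but it can also grow. These are contacts, not money. Without unit prices and each component's share of total cost, the effect on the cost endpoint cannot be sized.

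**The case against.** The strongest reply is that criterion 7 already deals with this: a patient whose 6-month course cannot be seen is not enrolled, which is compatible with section 8.4. Section 8.6.1 also allows a physician's chart as source. The centre must have experience of NVAF care and of both treatments, which is consistent with follow-up there. The e-CRF, which holds the operational definitions, is not part of the document and may record outside care. The study is descriptive and exploratory.

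Much of this stands as a limit on what can be claimed. A reader might infer that outside care is counted as zero. No passage says so; that is only what would happen by default if costs were added up from the chart and *none* were not separated from *unknown*. A reader might take the requirement for "neurologists, who work in cerebrovascular center in a hospital" as confining the data to that unit's files. It is a condition for choosing the centre, and other records of the hospital are not excluded. Nor was the study set up to measure warfarin monitoring cost alone: the objective covers all direct costs in both arms. Finally, the documents do not say where INR is checked after discharge.

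The reply does not close the gap. Neither criterion 7 nor section 8.6.1 commits the study to obtaining outside records or to judging completeness, and the exploratory label does not make an understated cost a correct description.

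**Conclusion.** The concern holds in conditional form. The named source is hospital records at one centre, and the protocol does not say which records satisfy criterion 7 or how outside care is treated. If such care is not captured, direct costs are understated in both arms. Any missed INR check would fall on warfarin, but the size and the sign of the net bias in the arm difference are unknown because capture is not measured.

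A tempting stronger conclusion is that the design necessarily hides warfarin cost and so understates the saving with apixaban. The documents do not support that: visits and admissions can be missed in either arm, and in the illustration a true difference of 9 contacts can be recorded as low as 0 or as high as 11.25. Those figures rest wholly on assumed contact numbers and capture shares. The point should be settled before data collection; it does not invalidate the study.

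**What to change.** - In section 8.4, state which records satisfy criterion 7 and how completeness over the 6 months is judged.
- Add an e-CRF item: anticoagulation follow-up at the study hospital for the full 6 months (yes, no, unknown). For resource-use items, record *none* separately from *unknown*. Report both by arm.
- Keep the full analysis set as the main analysis. Beside it, show the cost comparison in patients with *yes* as a sensitivity analysis.
- Add a sensitivity analysis that values INR checks over a stated range of frequencies for warfarin patients followed elsewhere or with unknown follow-up.
- Word the conclusion as direct costs recorded at the study hospital, and list incomplete capture as a limitation in section 8.9.

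The cost is one extra field with the none/unknown coding, two additional tables and a narrower conclusion. No linkage to insurer data is needed. The restricted table will have fewer patients and may be selected, because the place of follow-up is determined after the index date and may differ by arm. For that reason it should stand beside the main analysis and not replace it.

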#### **8.5. Study size**

The study will be descriptive in nature. No sample size was statistically determined. Based on experience of experts on anticoagulant treatment the data from 120 patients per study arm can be collected.

#### **8.6. Data management**

The data will be transcribed by the physician to an anonymous electronic Case Report Form from the patient's medical records. The data will be obtained retrospectively and no patient data identification will be possible.

##### **8.6.1. Case Report Forms (CRFs)/Data Collection Tools (DCTs)/Electronic Data Record**

As used in this protocol, the term CRF should be understood to refer to either a paper form or an electronic data record or both, depending on the data collection method used in this study.

A CRF is required and should be completed for each included patient. The completed original CRFs are the sole property of Pfizer and should not be made available in any form to third parties, except for authorized representatives of Pfizer or appropriate regulatory authorities, without written permission from Pfizer. The investigator shall ensure that the CRFs are securely stored at the study site in encrypted electronic form and will be password protected to prevent access by unauthorized third parties.

The investigator has ultimate responsibility for the collection and reporting of all clinical, safety, and laboratory data entered on the CRFs and any other data collection forms (source documents) and ensuring that they are accurate, authentic/original, attributable, complete, consistent, legible, timely (contemporaneous), enduring, and available when required. The CRFs must be signed by the investigator or by an authorized staff member to attest that the data contained on the CRFs are true. Any corrections to entries made in the CRFs or source documents must be dated, initialed, and explained (if necessary) and should not obscure the original entry.

In most cases the source documents are the hospital or the physician's chart. In these cases, data collected on the CRFs must match those charts.

In some cases, the CRF may also serve as the source document. In these cases, a document should be available at the investigator site and at Pfizer that clearly identifies those data that will be recorded on the CRF, and for which the CRF will stand as the source document.

### **8.6.2. Record Retention**

To enable evaluations and/or inspections/audits from regulatory authorities or Pfizer, the investigator agrees to keep records, including the identity of all participating patients (sufficient information to link records, e.g., CRFs and hospital records), all safety reporting forms, source documents, detailed records of treatment disposition, and adequate documentation of relevant correspondence (e.g., letters, meeting minutes, and telephone call reports). The records should be retained by the investigator according to local regulations or as specified in the clinical study agreement (CSA), whichever is longer. The investigator must ensure that the records continue to be stored securely for so long as they are retained.

If the investigator becomes unable for any reason to continue to retain study records for the required period (e.g., retirement, relocation), Pfizer should be prospectively notified. The study records must be transferred to a designee acceptable to Pfizer, such as another investigator, another institution, or to an independent third party arranged by Pfizer.

Investigator records must be kept for a minimum of 15 years after completion or discontinuation of the study or for longer if required by applicable local regulations.

The investigator must obtain Pfizer's written permission before disposing of any records, even if retention requirements have been met.

### **8.7. Data analysis**

The statistical analyses will be descriptive and exploratory. Given the nature of the study, which is exploratory, it is not designed to confirm or reject predetermined hypotheses.

Categorical outcomes will be summarized by the number and percentage in each category. Continuous outcomes will be summarized by mean, standard deviation, median, minimum and maximum values.

All analyses will be based on the full analysis set, comprising all subjects enrolled into the study.

The paired tests will be applied in the detailed analyses. Relevant endpoints will be compared using the differences in mean / median or proportion. Statistical significance will be assessed at a significance level of 0.05. All statistical analyses will be conducted using STATA version 13.1.

**Table 2:** Table of descriptive analyses

Variable	Categorical outcome	Continuous outcome
Age		X
Sex	X	
Body height, weight, BMI		X
Period between stroke/TIA and start of secondary stroke prevention (duration in days)		X
Period between stroke/TIA and start of secondary stroke prevention (medication)	X	
CHA2-DS2-VASc Score		X
Stratification: (0, 1, 2-9)	X	
HAS-BLED Score		X
Stratification: (0-2, 3-9)	X	
Warfarin/apixaban dosage		X
INR measurements	X	
Number and type of outpatient visits, diagnostic procedures, labs, hospital admissions	X	
Cost of outpatient visits, diagnostic procedures, labs, medication, hospital admissions		X
Amount, type and severity of ischemic events	X	
Cost of ischemic events		X
Amount, type, severity of major/minor hemorrhagic events	X	

Cost of major/minor hemorrhagic events		X
Adverse events	X	

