## 7. RESEARCH QUESTION AND OBJECTIVES

The primary objective of the study is:

- Description of direct costs related to warfarin/apixaban treatment during the first 6 months of the secondary stroke prevention in NVAF patients.

The secondary objectives of this study are:

- Comparison of direct costs related to warfarin/apixaban treatment during the first 6 months of the secondary stroke prevention in NVAF patients;
- Number of hospitalization days in the first 6 months of the treatment;
- Number of ischemic/hemorrhagic strokes in the first 6 months of the treatment;
- Number of ischemic events in the first 6 months of the treatment;
- Number of major/minor hemorrhagic events in the first 6 months of the treatment;
- Mortality rates in both cohorts;
- Number and costs of medical procedures directly related to the treatment in the first 6 months (visits, hospitalizations, labs, diagnostics, etc.);
- Overall safety (adverse events) of the treatment.

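### Section 8.7 specifies paired tests, but two unmatched cohorts followed over a single 6-month period contain no pairs

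*Combined protocol and SAP*

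**What the plan says.** Section 8.7 describes the analyses as descriptive and exploratory, then states "The paired tests will be applied in the detailed analyses". It goes on to say that relevant endpoints are compared by differences in means, medians or proportions, at a significance level of 0.05. It names no specific test, pairing variable or matching rule, and it does not define which analyses are the detailed ones. The same section says "All analyses will be based on the full analysis set, comprising all subjects enrolled into the study".

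The design is set out in sections 8.1 to 8.3:

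- Groups: "The study follows two cohorts of NVAF patients, who used either warfarin or apixaban as a secondary stroke/TIA prevention".
- Enrolment: "the data collection will be closed as soon as there are 120 patients enrolled in each study arm".
- Observation window: "Consecutive data of the 6 months after the first prescription of warfarin/apixaban".
- Outcome in Table 1: "Number and type of resource use during the first 6 months of warfarin/apixaban treatment".

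The first secondary objective in section 7 is "Comparison of direct costs related to warfarin/apixaban treatment during the first 6 months of the secondary stroke prevention in NVAF patients".

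**The concern.** A paired t-test, a signed-rank test and a McNemar test each need a link between individual observations: a matched partner, or the same patient measured twice. If the plan supplies neither, the test it names is undefined until someone chooses the pairs.

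Point estimates are not at stake, but standard errors, confidence intervals and p-values are. A result near 0.05 in the secondary cost comparison could not be reproduced by a second analyst who lacked the first analyst's pairing. If the arms ended unequal, a paired test would also have to leave patients out, contrary to the full analysis set in the same section.

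**Working it through.** **Step 1. Look for pairs in the design.** The plan derives no sample size or power figure (section 8.5), so there is no figure to reproduce. The first check is of the text.

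- *Between patients.* The two cohorts consist of different patients (8.1), new to anticoagulation for NVAF (8.2.1), and are filled by count (8.2). No matching variable, ratio or propensity score appears. Section 8.9 counts it as a strength that patients are not selected by subgroup.
- *Within patients.* Resource use is recorded for the first 6 months of treatment only (8.1, 8.3). Table 1 also records therapy between the index event and anticoagulation, but as exposure. No outcome is listed at two time points.

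Neither kind of pair exists.

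**Step 2. What pairing changes, with n per arm.**

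- Mean difference: the mean of the paired differences equals the difference of the arm means, whatever the pairing. The same holds for proportions, and arm medians do not involve pairing. A median of paired differences does.
- Standard error: Welch SE² = (s₁² + s₂²)/n; paired SE² = (s₁² + s₂² − 2s₁₂)/n. With equal variances the ratio of SEs is √(1 − r), where r is the correlation that the chosen pairing happens to produce.
- Under random pairing r has SD of about 1/√119 = 0.092, so a 95% range of about ±0.18. That gives ratios from √0.82 = 0.91 to √1.18 = 1.09.

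**Step 3. Size for costs.** The documents give no cost SD. Assumed: 120 per arm, lognormal costs, CV 1.0 / 1.5, two-sided 0.05, random pairing.

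| Quantity | CV 1.0 | CV 1.5 |
|---|---|---|
| Paired SE / Welch SE, 95% range | 0.90–1.07 | 0.89–1.06 |
| Type I error, paired t (20,000 null data sets) | 0.046 | 0.046 |
| Type I error, Welch | 0.046 | 0.045 |
| Paired t and Welch disagree at 0.05, null | 0.8% | 0.7% |
| Pairings with paired-t p < 0.05 when Welch p = 0.051 | 38% | 35% |
| … when Welch p = 0.06 | 14% | 13% |
| … when Welch p = 0.07 | 5% | 5% |
| … when Welch p = 0.10 | 0.3% | 0.5% |
| Two pairings, opposite paired-t verdicts: null | 1.0% | 1.1% |
| … true cost ratio 1.25 | 4.1% | 2.8% |
| … true cost ratio 1.4 | 3.0% | 3.6% |
| Two pairings, opposite signed-rank verdicts: null | 3.3% | 3.7% |
| … true cost ratio 1.25 | 12.4% | 11.3% |
| … true cost ratio 1.4 | 7.3% | 12.5% |

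**Step 4. Size for proportions.** Let k be the number of pairs in which both members have an event. Under random pairing k is hypergeometric, and the discordant counts are a − k and b − k.

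Example with 24 vs 12 events. At k = 2 the discordant counts are 22 and 10. Exact McNemar gives p = 0.0501; the asymptotic version gives (22 − 10)²/32 = 4.50, p = 0.034. At k = 3 (21 and 9), exact p = 0.043. So exact McNemar is below 0.05 only when k is 3 or more, which happens in 44% of pairings. The asymptotic version is below 0.05 even at k = 0: (24 − 12)²/36 = 4.00, p = 0.0455.

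| Events of 120 | Chi-square p | Fisher p | Exact McNemar < 0.05 | Asymptotic McNemar < 0.05 |
|---|---|---|---|---|
| 24 vs 12 | 0.030 | 0.046 | 44% | 100% |
| 23 vs 12 | 0.044 | 0.066 | 5% | 72% |
| 22 vs 12 | 0.064 | 0.095 | 0.1% | 15% |

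The asymptotic version has no continuity correction. The plan names neither version.

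**The case against.** The strongest reply is that nobody would invent random pairs. The word is probably a slip for two-sample or pairwise: the next sentence of section 8.7 speaks of differences in means, medians and proportions, which is ordinary two-group language. On that reading the instability above never arises. On the literal reading, type I error is still nominal and the paired t-test changes the verdict in only a few percent of data sets. The larger signed-rank and McNemar figures belong to tests the plan does not name. The study is exploratory, its primary objective is descriptive, and no power claim depends on the test.

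Most of this stands, and it limits the weight of the point. It does not remove it. Under the slip reading the plan still names the wrong family of tests, and nothing else in the document says which tests will be run.

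The conflict with the full analysis set is also conditional: it needs the literal reading and unequal arms. Unequal arms are possible, since section 8.2 says "If there are not 120 patients enrolled in each study arm after 3 months of the data collection, the period can be prolonged", to at most 6 months, and does not say what happens if an arm is still short.

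A further objection is sound: offering a choice of Fisher or chi-square would leave the same looseness, because 23 vs 12 events gives p = 0.066 with one and 0.044 with the other. The correction should name one method per endpoint type.

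**Conclusion.** The concern holds and should be fixed. The mismatch between the named tests and the design is certain from the text. Which reading the authors intended is not.

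If the word is a slip, the cost is one wrong word. If it is literal, verdicts become arbitrary in a narrow band around 0.05: for the paired t-test roughly up to a Welch p of 0.07, and more widely for signed-rank and McNemar tests. With equal arms, estimated differences in means, proportions and arm medians are unaffected, and so is the primary objective.

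The sizes rest on assumed lognormal costs, assumed CVs, illustrative event counts and random pairing. They show the scale of the problem and are not forecasts for this study.

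**What to change.** Replace the sentence in section 8.7 with independent-sample comparisons, list the endpoints that make up the detailed analyses, and name one method for each type. One workable set:

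- Costs: difference in means with a Welch 95% confidence interval and test.
- Counts such as hospital days and visits: difference in medians, with the Mann-Whitney test.
- Proportions: difference with a 95% confidence interval and Fisher's exact test.
- All p-values two-sided and labelled nominal.

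Other choices are defensible (a bootstrap interval for costs, chi-square for proportions), provided one is fixed in advance.

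If matching was intended, state before data collection the matching variables, the ratio and the handling of unmatched patients, reconcile this with the full analysis set, and use paired tests only on the matched pairs. That would be a design change rather than a wording correction.

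The first option costs one or two sentences. It needs no new data and no change to Table 2, and it keeps every enrolled patient even if the arms end unequal. It does not address confounding between the arms, which is a separate matter.
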